At all visits and phone contacts (except for visits to apply a CGM sensor), the Investigator or designee will review glucose results (especially focusing on hypoglycemia), adverse events, changes in concomitant medications, and changes in IP and bolus insulin use. At all study visits, the following procedures will be performed: vital signs, body weight, urinalysis, urine pregnancy testing for women of childbearing potential, and an FBG test.

Additional procedures at study visits are as follows: at Weeks 8, 16, and 26, blood for HbA1c will be collected; at Weeks 12 and 26, subjects will wear their CGM sensor to the site for the staff to safely remove it; they will bring their Mealtime & Insulin Dose Record for the site staff to review, and blood will be collected for routine hematology and chemistry, TSH and free T4; at Weeks 12 and 26, blood will be collected for AIA; and at Week 26, a 12-lead ECG and physical examination will be performed. A subset of additionally consented subjects will have blood drawn at Day 1 and Weeks 2, 4, 8, 12, 16, 20, and 26 for optional pharmacokinetics (PK) (insulin glargine, M1, and M2 concentrations).

If a subject discontinues the study prematurely (early termination – ET), site personnel will make a reasonable effort to perform all study activities scheduled for Visit 9 (end of treatment – EOT visit). Additionally, it is also very important for site personnel to encourage subjects to visit the site at Week 26 ± 4 weeks (and Week 12 ± 1 week, if applicable) for a blood sample to be obtained for AIA and HbA1c measurements.

Site personnel will contact the subjects by telephone approximately 30 days after study completion to query for serious adverse event information only.

Subjects will only be included in the optional PK portion of the study if they are able to provide a baseline PK sample.

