At all planned visits and phone contacts (except for visits to apply a CGM sensor) the Investigator or designee will review glucose results (especially looking for hypoglycemia), adverse events, changes in concomitant medications, and changes in IP or bolus insulin use, and the following procedures will be performed: vital signs, body weight, urinalysis, urine pregnancy testing for women of childbearing potential, and an FBG test.

[figure not shown]
Additional procedures at study visits are as follows: at Weeks 8, 16 and 26, blood for HbA1c will be collected; during the visits at Weeks 12 and 26, subjects will wear their CGM sensors to the site for the site staff to safely remove it, and they will bring their Mealtime & Insulin Dose Record for the site staff to review, and blood will be collected for routine hematology and chemistry testing, TSH and free T4 and TSH; at Weeks 12 and 26, blood will be collected for AIA; and at Week 26, a 12-lead ECG and physical examination will be performed.

A subset of additionally consented subjects will have blood drawn at Day 1 and Weeks 2, 4, 8, 12, 16, 20, and 26 for optional PK (insulin glargine, M1, and M2 concentrations).

If a subject discontinues the study prematurely, site personnel will make a reasonable effort to perform all study activities scheduled for Visit 9 (end of treatment [EOT] visit).

Additionally, it is very important for site personnel to encourage subjects to visit the site at Week 26 ( $\pm$  4 weeks) (and Week 12  $\pm$  1 week if applicable) for a blood sample to be obtained for AIA and HbA1c measurements.

Figure 1 and Table 1 show the study design and study-related procedures, respectively.

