7.4 Exploratory

1) Continuous Glucose Monitoring Device Day of Wear

The day of wear will be defined as starting exactly $(x-1)*24$ hours and ending $x*24$ hours after the time of the first assessment at the given visit, where x is the day of wear from 2 to 8 days.

2) Time in hypoglycemia

The time in hypoglycemia will be defined using the CGM data from days 2 through 8 of wear at each of the 3 visits where CGMs are applied as the sum of the time where the glucose value is <3.0 mmol/L.

PPS will be used for some sensitivity analyses (for example, the primary endpoint for immunogenicity [from Section 11.6.1.3] and HbA1c [from Section 11.7.1.3]).

A second Per Protocol Analysis Set (PPS2) will be composed of all subjects whose treatment assignment was randomized, who received at least 1 partial dose and do not have any immunogenicity-interfering important protocol deviations (IIIPD) as defined in Section 11.3 up to visit Week 26. A third Per Protocol Analysis Set (PPS3) will be composed of all subjects whose treatment assignment was randomized, who received at least 1 partial dose and do not have any efficacy-interfering important protocol deviations (EIIPD) as defined in Section 11.3 up to visit Week 26. Subjects in the PPS2 and PPS3 will be grouped according to actual treatment received. The PPS2 and PPS3 are larger and less restrictive analysis sets than the PPS and will be used for some sensitivity analyses for the primary endpoint for immunogenicity [from Section 11.6.1.3] and HbA1c [from Section 11.7.1.3], respectively.

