11.6.1.3 Sensitivity Analyses

Inherent in the primary endpoint analysis described above are several implicit assumptions that can possibly affect the generalizability of immunogenicity. There are four assumptions that are important to mention. The primary analysis assumes that the impact on the immunogenicity conclusion of early discontinuations, important protocol deviations, less than full treatment duration and patterned missing data is negligible. Although the scientific rationale to make these assumptions is reasonable, sensitivity analyses for the primary endpoint of immunogenicity to assess the impact of these effects are planned, as follows:

- 1) Composite Strategy: Subjects in the SS with the intercurrent event of discontinuing treatment will be considered as having a treatment-induced AIA. Results of assessment after the end of treatment are excluded from the analysis. The imputation approach as described in Table 4 will be used for missing data. This sensitivity analysis will examine the assumption that results were not impacted by the discontinuation of treatment (as these will be imputed as positive immune response).
- 2) Per Protocol Analysis Set (PPS): Subjects with any important protocol deviations (as defined in Section 11.3) will be excluded from the analysis. For subjects in the PPS, the imputation approach as described in Table 4 for primary analysis will be followed. In the primary analysis, subjects with important protocol deviations could falsely draw the estimated treatment difference closer. Exclusion of these subjects in this sensitivity analysis will help assess the magnitude, if any, of this effect.
- 3) SS – Completers: This analysis will not use any imputation of missing data. Only subjects with valid baseline and visit Week 12 and Week 26 assessments conducted within the required visit window (visit Week 12 \pm 1 week and visit Week 26 \pm 4 weeks, respectively) and who had treatment until visit Week 26 will be used for the analysis. Subjects with less than a full treatment duration could underestimate the proportion of subjects reporting positive immune response. By including only completers, as in this sensitivity analysis, this estimated treatment difference is determined only by subjects whose treatment duration was full.

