11.7.1.3 Sensitivity Analyses

To evaluate the impact of important protocol deviations and missing data, sensitivity analyses will be performed using the analysis methods described for the FDA equivalence and EMA non-inferiority analyses:

- 1) PPS: Using MI approach as described for main HbA1c analysis. If in the number of subjects who discontinued treatment and return to provide an HbA1c sample at Week 26 is insufficient to perform the MI, the MI will instead be performed using data from all patients with HbA1c results at Week 26 in each treatment group under the assumption of MNAR. (Table 5, Analysis 2)
- 2) FAS Completers: This analysis will not use any imputation of missing data. Only subjects with valid baseline and visit Week 26 assessment conducted at actual visit Week 26 visit and who had treatment until visit Week 26 will be used for the analysis. (Table 5, Analysis 3)
- 3) Per Protocol Analysis Set 3 (PPS3) - Subjects with any efficacy-interfering important protocol deviations (EIIPD; as defined in Section 11.3) will be excluded from the analysis. For the subjects in the PPS3, the imputation approach as described for the main analysis will be followed. In the main analysis, subjects with efficacy-interfering important protocol deviations could falsely draw the estimated treatment difference closer. Exclusion of these subjects in this sensitivity analysis will help assess the magnitude, if any, of this effect. (Table 5, Analysis 4)

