3. STUDY DRUG	A temperature excursion occurred and the proper notification, quarantine and release	No	9	No	No

Sponsor: Gan & Lee Pharmaceuticals USA Corporation
Protocol no: GL-GLAT1-3001

PRA HEALTH SCIENCES

Statistical Analysis Plan
Version Date: 27-May-2021

Type of Deviation/ Code	Deviation Description	Important protocol deviation	Sub-Category	PD Effect on Immunogenicity	PD Effect on Efficacy
4. ASSESSMENT - SAFETY	Failure to complete single or multiple safety assessments (hematology, chemistry, thyroid labs, urinalysis, pregnancy test, vital signs, body weight, ECG, PE) at the final or Early Termination (ET) visit.	Yes	7	No	No
4. ASSESSMENT - SAFETY	AEs not assessed at a study visit (excluding hypoglycemia and not clinically significant hyperglycemia).	Yes	8	No	No
4. ASSESSMENT - SAFETY	Subject becomes pregnant during the study and is not withdrawn from the study.	Yes	9	No	No
4. ASSESSMENT - SAFETY	Partner of a male subject becomes pregnant during the study and pregnancy not reported.	Yes	10	No	No
4. ASSESSMENT - SAFETY	Failure to repeat laboratory tests for unexplained abnormal laboratory test results.	No	11	No	No
4. ASSESSMENT - SAFETY	A failure to complete multiple safety assessments (hematology, chemistry, thyroid labs, urinalysis, pregnancy test, vital signs, body weight) at a single visit.	Yes	12	No	No
4. ASSESSMENT - SAFETY	Failure to complete urine pregnancy test for all women of childbearing potential at study visit(s) and confirmed pregnancy later.	Yes	13	No	No
4. ASSESSMENT - SAFETY	Failure to follow the protocol (or any safety related plans) such that the safety of the subject or other subjects in the study is significantly impacted.	Yes	14	No	No
5. ASSESSMENT - EFFICACY	Failure to complete any efficacy assessments at study visits.				
5. ASSESSMENT - EFFICACY	Failure to complete HbA1c and/or Fasting Blood Glucose sampling at two consecutive visits, or at Baseline (Screening or Day 1), or at V9/Early Termination.	Yes	1	No	Yes
5. ASSESSMENT - EFFICACY	Failure to complete HbA1c and/or Fasting Blood Glucose sampling at a visit other than at Baseline (Screening or Day 1), or at V9/Early Termination.	No	2	No	No
6. VISIT WINDOW	Whole visit missed on or out of visit window.				
6. VISIT WINDOW	Missing an entire visit	No	1	No	No
6. VISIT WINDOW	Visit or procedure out of window	No	2	No	No
7. INFORMED CONSENT (ICF)	ICF process not conducted per ICH/GCP Guidelines or CFR.				

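### A missed fasting glucose sample alone removes subjects with complete HbA1c from PPS3, the per-protocol set built for the HbA1c sensitivity analysis

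*SAP*

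**What the plan says.** **The row.** SAP Appendix 4, category 5 (Assessment - Efficacy), sub-category 1 reads "Failure to complete HbA1c and/or Fasting Blood Glucose sampling at two consecutive visits, or at Baseline (Screening or Day 1), or at V9/Early Termination". It is graded important: Yes; effect on immunogenicity: No; effect on efficacy: Yes. Sub-category 2 covers "Failure to complete HbA1c and/or Fasting Blood Glucose sampling at a visit other than at Baseline (Screening or Day 1), or at V9/Early Termination" and is graded No throughout.

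**What the efficacy grade means.** SAP 11.3 splits important deviations by whether they are thought to interfere with HbA1c. Those that are become efficacy-interfering deviations, listed in Appendix 4, and they decide who leaves PPS3. The PPS3 definition (SAP 8.3) keeps subjects who "do not have any efficacy-interfering important protocol deviations (EIIPD) as defined in Section 11.3 up to visit Week 26". The same section describes PPS3 as larger and less restrictive than PPS and assigns it to the HbA1c sensitivity analysis.

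**How PPS3 is analysed.** SAP 11.7.1.3, item 3: "For the subjects in the PPS3, the imputation approach as described for the main analysis will be followed".

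**The sampling schedule.** Protocol 8.1: "at Weeks 8, 16 and 26, blood for HbA1c will be collected"; with Screening, that makes four HbA1c samples. The Protocol synopsis lists for all study visits "urine pregnancy testing for women of childbearing potential, and an FBG test". Protocol 9.2 shows an FBG but no HbA1c on Day 1.

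**The FBG endpoint.** SAP 11.7.2.1 analyses it in the FAS and counts a missing Week 26 value as not achieving control. The supplied text plans no per-protocol FBG analysis.

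**The concern.** The row joins two tests with and/or, while the grade it carries is defined by one of them. FBG is drawn at all nine clinic visits and does not enter the HbA1c model, so a subject can have every HbA1c sample and still leave PPS3 because of glucose sampling.

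PPS3 is there to show whether deviations that matter for HbA1c made the arms look more alike than they are. If it also drops subjects for an unrelated reason, it loses valid HbA1c data. Any shift between the FAS and PPS3 results then mixes the effect of real HbA1c deviations with that of an irrelevant exclusion.

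Two smaller points sit in the same row. The phrase about two consecutive visits does not match a test that is never drawn at adjacent clinic visits. And the Visit 9/early termination clause removes some subjects before the planned imputation is applied.

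**Working it through.** The plan states no figure for this rule, so there is none to reproduce. The check has two parts: apply the row to the schedule, then size the FBG clause under an assumed miss rate.

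**1. The row against the schedule**

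Inputs: HbA1c at V1 (Screening), V5 (Week 8), V7 (Week 16) and V9 (Week 26); FBG at V1 to V9 (Protocol Table 1 and Section 9).

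| Pattern | Leaves PPS3? |
|---|---|
| HbA1c complete, one FBG missed at V9/ET | Yes |
| HbA1c complete, one FBG missed at V1 or V2 | Yes, if either visit counts as baseline |
| HbA1c complete, one FBG missed at any of V3 to V8 | No |
| HbA1c complete, FBG missed at V3–4, V4–5, V5–6, V6–7 or V7–8 | Yes |
| FBG complete, HbA1c missed at Week 8 only or Week 16 only | No |
| FBG complete, HbA1c missed at both Week 8 and Week 16 | No if visits means clinic visits; yes if it means scheduled HbA1c samples |

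The gaps between HbA1c visits are 5−1 = 4, 7−5 = 2 and 9−7 = 2, so no two are adjacent clinic visits. Counted as scheduled samples, the pairs are V1–V5, V5–V7 and V7–V9. The first and last are already caught by the baseline and V9/ET clauses, so only Week 8 with Week 16 adds anything.

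**2. Possible size of the FBG clause**

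Assumption, not from the documents: each FBG is missed independently with probability q, over all nine visits, for q = 2%, 4% and 6%.

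The probability of no two adjacent misses among n visits is A(n) = Σ C(n−k+1, k) qᵏ(1−q)ⁿ⁻ᵏ. For n = 8 the coefficients are 1, 8, 21, 20, 5; for n = 6 they are 1, 6, 10, 4.

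- Both baseline samples must be missed (itself an adjacent pair): P = 1 − (1−q)·A(8).
- Either baseline sample is enough: P = 1 − (1−q)³·A(6).

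| q | A(8) | P, both | A(6) | P, either |
|---|---|---|---|---|
| 2% | 0.99725 | 1 − 0.98×0.99725 = 2.3% | 0.99803 | 1 − 0.94119×0.99803 = 6.1% |
| 4% | 0.98921 | 1 − 0.96×0.98921 = 5.0% | 0.99226 | 1 − 0.88474×0.99226 = 12.2% |
| 6% | 0.97621 | 1 − 0.94×0.97621 = 8.2% | 0.98290 | 1 − 0.83058×0.98290 = 18.4% |

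On 550 planned subjects the ends of the ranges are about 12 to 45 (both) or 33 to 101 (either).

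These figures count subjects who meet the FBG clause. At V1, V5, V7 and V9 both tests are venous samples, so one missed draw may lose both, and such a subject is not an HbA1c-complete loss. At V2, V3, V4, V6 and V8 no HbA1c is scheduled, so a miss there is FBG only.

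**The case against.** **Only supportive work is affected, and the definitions may be fuller elsewhere.** Both parts stand. The main HbA1c analysis uses the FAS. SAP 11.3 leaves the definition of important deviations to a guidance document that is not supplied, and requires the per-protocol sets to be finalised before database lock. That document could narrow the row, but the grade printed in Appendix 4 decides PPS3 as the SAP is written.

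**PPS is strict by design.** Protocol 12.5.3 excludes any important deviation from PPS, and SAP 11.6.1.3 repeats it: "Subjects with any important protocol deviations (as defined in Section 11.3) will be excluded from the analysis". Losing a subject from PPS over a missed FBG follows from that choice. This stands, so the point is limited to PPS3.

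**The size is assumed.** This stands too. The documents give no miss rate, misses need not be independent, and a sample drawn from a subject who had not fasted may not count as failed sampling.

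A reader might also infer three stronger things, which the documents do not support:

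- *That the row removes most of the subjects whose HbA1c would be imputed, so that PPS3 nearly repeats the completers analysis.* The clause excludes those with no HbA1c at V9 or early termination. Protocol 9.11 calls for Visit 9 activities at an early termination visit, so a subject who withdraws early and gives that sample does not meet the V9/ET clause and is imputed if there is no Week 26 value. The completers analysis also requires treatment until Week 26, which PPS3 does not. Requiring an outcome sample for per-protocol membership is a debatable choice, not an error.
- *That the row contradicts category 6, where "Missing an entire visit" is graded not important.* PPS3 excludes on any efficacy-interfering deviation, so a No row does not cancel a Yes row that the same subject meets.
- *That the Week 8 and Week 16 gap weakens the HbA1c result.* It exists on only one reading of the phrase. The ANCOVA models Week 26 change with baseline as covariate, the displayed imputation code uses treatment, baseline and Week 26 only, and the repeated-measures model that uses the interim values runs on the FAS.

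**Conclusion.** The point holds for PPS3. Appendix 4 attaches an HbA1c-based grade to a row that FBG alone can trigger, so PPS3 can lose subjects with complete HbA1c, and the FBG endpoint gains nothing from it.

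The number affected cannot be derived from the documents. Under independent misses at 2–6% of visits it is roughly 2–8% of subjects if both baseline FBGs must be missed, or 6–18% if either is enough. The spread between those readings shows that the baseline clause also needs to be pinned down.

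The wording on consecutive visits is a clarification with little numerical consequence. The V9/ET clause needs a note on who is left to impute; it need not be deleted. The main HbA1c conclusion is untouched. This is worth correcting, but it does not threaten the trial's primary or key secondary inference.

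**What to change.** Before database lock, split Appendix 4, category 5, sub-category 1 into two rows:

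- **HbA1c sampling missed** at Screening, at V9/early termination, or at both Week 8 and Week 16. Keep the present grades (important: Yes; immunogenicity: No; efficacy: Yes). This states consecutive visits as scheduled HbA1c samples and drops Day 1, when no HbA1c is drawn.
- **FBG sampling missed with HbA1c complete**, for the patterns now listed. Grade efficacy: No. Leaving it graded important keeps PPS as the protocol defines it. State whether baseline means both samples missed or either one.

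Add a sentence to SAP 11.7.1.3, item 3: subjects with no HbA1c at V9/early termination leave PPS3 under this rule, so the imputation covers only those who remain without a Week 26 value. Report, by arm, how many subjects each clause excludes and how many are imputed.

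The cost is one edited row, one sentence and a re-derivation of PPS3. No new data are needed, and the FAS analyses do not change.
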